fMRI Heat Pain Protocol. Three task-based fMRI runs will be conducted subsequent to resting-state scanning using a noxious thermal stimulation protocol. This protocol has been previously used in an NIH-funded study in which [name] is a co-investigator (R01AT006334). For this task, a long MR-compatible thermal probe attached to a Medoc Q-Sense fMRI compatible thermal stimulator will be used to deliver noxious thermal stimuli. Blocks of thermal stimuli will be delivered to the glabrous skin of the foot at the individually calibrated temperature determined during the screening visit. Following each thermal stimulation block, participants will rate levels of pain intensity and perceived relief from alcohol. Each block will be preceded and/or followed by a 30-second rest blocks. An electronic VAS will be presented following each thermal stimulation block for the purposes of rating pain intensity (anchored from "No pain at all" to "Most intense pain imaginable"). After each run, participants will rate their perceived degree of relief from pain as a result of consuming their beverage using an electronic

VAS anchored from “No relief at all” to “Most profound relief imaginable”. Runs will last for approximately 6 minutes, and will take place consecutively.

Power Analysis. Power analysis and recruitment goals are based on results of our pilot study (see attached grant document for a detailed description of results). Power analyses were performed assuming two-tailed hypothesis tests. Effect sizes are reported as Cohen’s d, r, or f^2 (Cohen, 1988).

Our pilot data suggested statistically large increases in pain threshold temperature ($d = 1.16$) associated with BrACs $\sim .052$ g/dL. Effects on pain tolerance temperature and intensity ratings were smaller ($d = .28$); however, our targeted sample of 110 completers will provide $\sim 80\%$ power these effects, and $> 99\%$ power to detect effects of alcohol on pain threshold.

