FH of alcoholism was associated with greater expectancy of pain relief from alcohol intake in our pilot work ($d = 1.12$), as well as lower ratings of pain relief ($d = .54$). Effects of sex on these measures were large ($d > .88$). Sex also appeared to be a potent moderator of alcohol analgesia ($d > .90$), with women showing stronger analgesic effects. Our sample will provide $> 80\%$ power to detect these effects. FH was associated with smaller effects on alcohol-related reductions in pain intensity ($d = .42$), as well as pain threshold and tolerance ($d < .26$), resulting in $\sim 54\%$ power to detect interactive effects of FH and dose on these measures.

Across participants, preliminary data suggested small-to-moderate correlations between expectancy of pain relief from alcohol, ratings of pain relief, and typical daily drinking and reductions in pain sensitivity ($.26 < r < .44$). We anticipate $\sim 80\text{-}99\%$ power to detect these effects. However, our data also suggested that sex and FH may moderate these relationships. The interaction of sex and expectancy of pain relief strongly predicted increases in pain threshold and tolerance associated with alcohol intake ($f^2 > 1.11$). A similar effect was detected for the interaction of FH and expectancy of pain relief ($f^2 > .81$). A weaker interaction of FH and ratings of relief on QST measures was also detected ($f^2 > .37$). Likewise, interactions of sex with typical daily drinking and ratings of relief showed some relation to QST changes ($f^2 < .21$). We anticipate $> 94\%$ power to detect each of these interactions. There was little evidence of Sex or FH interactions with typical drinking on alcohol analgesia ($f^2 < .04$). Effect sizes of FH X Sex X expectancy/relief/typical drinking interactions could not be assessed given our limited sample; however, we anticipate sensitivity to detect an interactive $f^2 > .14$ with 80% power given our recruitment target.

Data Analysis Strategy. Data will be analyzed using SPSS 24 (IBM Corp., Armonk, NY).

Aim 1. Test competing hypotheses regarding the effects of family history of alcoholism on alcohol analgesia. To assess hypotheses related to Aim 1, FH status will be included as an independent variable in repeated measures general linear models analyses (rmGLM; SPSS GLM procedure; repeated: dose), with pain threshold/tolerance and intensity ratings, associated relief ratings, expectancy of pain

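### One power figure of about 54% is given for FH by dose on all three pain measures; it fits pain intensity (d = .42), but threshold and tolerance (d < .26) have about 25–27% at most on the plan's own scale

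*Combined protocol and SAP*

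**What the plan says.** All of this is in section 6 of the combined protocol and SAP.

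- Power Analysis, general: "Power analyses were performed assuming two-tailed hypothesis tests". Effect sizes are given as Cohen's d, r or f², with no statement of whether d for a within-person effect is in SDs of the change or in raw SDs. For pilot details the reader is told to "see attached grant document for a detailed description of results".
- Power Analysis, dose effect: pilot effects on tolerance temperature and intensity ratings were d = .28, and "our targeted sample of 110 completers will provide" about 80% power for them. The dose effect on threshold was d = 1.16, with power above 99%.
- Power Analysis, FH by dose: d = .42 for reduction in pain intensity and d < .26 for threshold and tolerance, followed by about 54% "power to detect interactive effects of FH and dose on these measures". No separate figure is given for threshold or tolerance.
- Data Analysis Strategy, Aim 1: support for H1 is read from threshold, tolerance and intensity together. The text calls this a main effect of FH on the magnitude of analgesia. Because that magnitude is an alcohol-versus-placebo difference, I take it to be the FH-by-dose interaction of the repeated-measures model.
- Data Analysis Strategy, Aim 3: sex enters the same models.

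**The concern.** Power rises with the effect size, and .42 is about 1.6 times .26. A single figure of 54% therefore cannot describe both unless the two d values are on different scales, which the plan does not say.

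This bears on how results for H1 will be read. A reader of the current text expects roughly even odds of detecting the pilot effect on each measure. If the true figure for threshold and tolerance is about a quarter, a non-significant result there is the expected outcome even when the FH effect is as large as the pilot bound.

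**Working it through.** **Inputs from the documents.** N = 110 completers; two-sided tests; FH by dose d = .42 (intensity) and d < .26 (threshold, tolerance); dose effect d = .28 with about 80% power; FH effect on relief d = .54 with more than 80% power; sex as moderator d > .90.

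**Assumptions.** Alpha is .05. The FH split is not given, so 55/55 to 37/73 is shown. As a starting point, d is in SDs of the alcohol-minus-placebo change.

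**Method.** With two dose levels, FH by dose is a two-sample t-test on each person's change. The noncentrality is λ = d × √(n₁n₂/(n₁+n₂)) with 108 df.

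**Step 1: the plan's other figures.**
- Dose effect, paired t: λ = .28 × √110 = 2.94, power 82.9% (plan: about 80%).
- FH on relief, 55/55: λ = .54 × √27.5 = 2.83, power 80.1% (plan: more than 80%).

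Both come out close to the plan. At alpha .10 they would be 89.9% and 87.9%, and at .01 they would be 62.4% and 58.4%, so .05 is the level that fits.

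**Step 2: FH by dose.**

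| FH split | d = .42 | d = .26 |
|---|---|---|
| 55/55 | 58.8% | 27.2% |
| 40/70 | 55.6% | 25.5% |
| 37/73 | 54.1% | 24.8% |

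At 55/55, λ = .42 × 5.244 = 2.20 and .26 × 5.244 = 1.36. The stated 54% is acceptable for intensity and about twice the computed power at d = .26. Since the plan says d is below .26, the last column is an upper limit for this model. At d = .20 power is 18.0% (55/55).

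**Step 3: a check that does not need the split, N or scale.** On any common scale the two noncentralities stand in the ratio .42/.26 = 1.615. Power of 54% corresponds to λ = 2.079.
- If that belongs to d = .26, then d = .42 has λ = 2.079 × 1.615 = 3.36, power 91.4%.
- If it belongs to d = .42, then d = .26 has λ = 2.079 / 1.615 = 1.29, power 24.7%.

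**Step 4: raw-SD scale.** If d is in raw SDs with within-person correlation r, the change-scale effect is d / √(2(1−r)).

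| r | dose effect, d = .28 | FH by dose, d = .42 | FH by dose, d = .26 |
|---|---|---|---|
| .46 | 80.0% | 55.6% | 25.5% |
| .50 | 82.9% | 58.8% | 27.2% |
| .785 | 99.3% | 91.4% | 54.0% |

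(FH by dose at 55/55.) Reaching 54% at d = .26 needs r of about .785, but the d = .28 dose effect would then have 99.3% power, not about 80%. The r that returns about 80% puts d = .26 back at 25.5–27.2%.

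**Step 5: sex in the model.** Removing a balanced sex effect of d = .90 multiplies d by √(1 + .90²/4) = 1.097, with 106 df. Power is then 31.6% at d = .26 and 66.8% at d = .42. Reaching 54% at d = .26 would need a sex effect of d = 2.30.

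**Step 6: more participants.** At d = .26 all 220 recruits (110/110) would give 48.4%; 54% needs 254 (127/127).

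**Step 7: precision.** The 95% CI half-width for the FH contrast is 1.982 × √(1/55 + 1/55) = .378 SD, or .400 SD at 37/73. Both exceed .26 SD.

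**The case against.** The strongest defence is that d may be in raw SDs. Each outcome then has its own within-person correlation, and no common scale is required: r of about .44 for intensity and .785 for threshold and tolerance would give 54% for all three. The d = .28 figure cannot exclude this for threshold, whose dose effect of d = 1.16 has power above 99% on any scale. The grant document that might settle the matter is not in the text. This stands as a limit: for threshold, the common scale is an assumption. It does not rescue tolerance, which the plan itself places at d = .28 with about 80% power. That anchor is also one figure for two measures, but both share the same d there, so pooling them causes no conflict.

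Two smaller points also have weight. The fit for intensity is approximate: with d taken directly and equal groups it is 58.8%, and the 37/73 split that gives 54.1% would leave the d = .54 relief effect at 75.6%, below the plan's figure. And sex, or other covariates named under Aim 1, could raise power above 27%; the sex effect at d = .90 takes it to about 32%.

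Finally, the plan already reports FH-by-dose power well below 80%, and it nowhere says that a null result on threshold or tolerance shows there is no FH effect. That limits the consequence. It does not make the stated figure right for those measures.

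**Conclusion.** The concern holds. About 54% is a fair figure for pain intensity (54–59% across the splits shown). For threshold and tolerance at d = .26 it should be about 25–27%, about 32% with sex in the model, and lower for smaller effects. A non-significant result on those two measures is then expected about 73–75% of the time, or about 68% with sex in the model, when the true effect equals the pilot bound. The likeliest explanation is that the intensity figure was applied to the other two measures, though the documents do not show this.

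The conclusion that one figure cannot serve both effect sizes needs only a common scale of d. The values themselves rest on alpha .05, the assumed FH split and, for threshold, the scale inferred from the d = .28 statement. Pilot effects were seen at a BrAC near .052 g/dL while the trial targets .08 g/dL, so true effects may differ. This should be corrected, but it does not undermine the design.

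**What to change.** In the Power Analysis, replace the single figure with separate FH-by-dose power for intensity and for threshold/tolerance. State alpha, the scale of d (with the within-person correlation if raw SDs were used), the assumed FH split and whether sex is in the model. If the grant document shows a different correlation for threshold, give it there.

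In the Aim 1 analysis, add one sentence: FH-by-dose estimates on threshold and tolerance will be reported with 95% confidence intervals, and a non-significant result will not by itself be read as absence of an FH effect.

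The cost is wording only, and a less favourable stated power on two measures. No FH quota, and no change to recruitment, completers, model or decision rule, is needed.

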General Approach. For this study of healthy, community-dwelling moderating drinkers, we propose a repeated-measures, double-blind placebo-controlled factorial design with FH of alcoholism (+/-) and sex as between-subjects factors and alcohol administration (Alcohol Dose: placebo, 0.08 g/dL) as a within-subject factor. The study will include equal numbers of men and women. Study procedures will occur in the Center for Pain Research and Behavioral Health of the University of Florida under supervision of the PI (JB). The investigative team, including the PI; Drs. [name], [name], and [name]; and research assistants, will meet on a bi-weekly basis over the course of the project to

ensure successful completion. Recent progress regarding all aspects of the study will be addressed during these meetings, including ongoing review of recruitment practices and behavioral and imaging data quality. Drs. [name], [name], [name], and [name] will also work together to ensure all research assistants are fully trained to conduct the project.

Methods

Participants. Healthy volunteers (N=220; 110 women) will be recruited for the study via flyers, word of mouth, and internet and local radio advertisements with the aim of obtaining 110 completers; 55 women). Individuals aged 21-45 years will be recruited in order to avoid confounding effects of binge-drinking patterns associated with college-aged individuals and the apparent increased susceptibility of older adults to the acute neurobehavioral effects of alcohol (e.g., [name] et al., 2014). We plan to enroll a representative sample of participants from our recruitment area in north central Florida (i.e., 65% white, 23% black, 7% Asian, 5% other), including ~10% identifying as Hispanic or Latino (see targeted recruitment table).

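### The > 94% power claim for the sex × typical drinking and sex × relief interactions rests on an upper bound (f² < .21), which cannot support a floor on power

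*Combined protocol and SAP*

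**What the plan says.** All the figures are in one paragraph of section 6, Power Analysis. It gives pilot effect sizes for interactions predicting change in the pain (QST) measures:

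- sex × expectancy of relief: f² > 1.11
- FH × expectancy of relief: f² > .81
- FH × relief ratings: f² > .37
- sex × typical daily drinking and sex × relief ratings: f² < .21, introduced by "Likewise, interactions of sex with typical daily drinking and ratings of relief showed some relation to QST changes"

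The paragraph then claims more than 94% "power to detect each of these interactions". The sentence after that reads "There was little evidence of Sex or FH interactions with typical drinking on alcohol analgesia", with f² < .04. The paragraph ends with a sensitivity statement for the three-way interactions: 80% power for f² above .14.

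The same section sets the sample ("our targeted sample of 110 completers will provide") and the sidedness ("Power analyses were performed assuming two-tailed hypothesis tests"). It names no alpha and refers the reader to an attached grant document for pilot details.

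The matching analyses are in Data Analysis Strategy, Aim 1. These are separate multiple regressions of alcohol analgesia on expectancies and on typical drinking, each with sex and FH interaction terms, followed by a simultaneous regression. Relief ratings appear under Aim 1 as a dependent variable of the repeated-measures models, not as a regression predictor.

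**The concern.** The first three interactions carry lower bounds. If the effect is at least .37, power is at least the power at .37, so a floor is legitimate. The sex × drinking and sex × relief pair carries only an upper bound. Any value from zero up to .21 satisfies it, and power over that range runs from alpha upward. A statement that power exceeds 94% cannot be derived from it.

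The f² < .04 sentence sharpens this for one of the two. Sex × typical drinking is first credited with a relation to QST change and more than 94% power, and is then grouped with interactions for which the pilot showed little. Aim 1 of the analysis section defines analgesia by pain threshold and intensity changes, so the two sentences appear to concern the same kind of outcome. The text names no measure that would separate them.

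At stake is how the sex-moderation terms in the Aim 1 regressions are read. Someone relying on the > 94% figure could give a null sex × typical drinking result more weight than the pilot figures allow.

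**Working it through.** **Inputs**

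- N = 110 completers (Power Analysis). Participants gives 220 recruited "with the aim of obtaining 110 completers", so no further allowance for dropout is needed.
- Two-tailed tests (Power Analysis).
- Alpha = .05. This is an assumption, because the power section states none; the only stated level is for the imaging analyses. Alpha = .10 is run as a sensitivity check.
- Model of 7 predictors: three main effects, three two-way terms and one three-way term. This count is inferred from the Aim 1 regression description, not stated. It hardly matters for the 1-df results.

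**Formula.** With u numerator df and p predictors, v = N − p − 1 and λ = f² × N. Power = P[F′(u, v, λ) > F(1−α; u, v)], where F′ is noncentral F. With p = 7, v = 110 − 7 − 1 = 102.

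**Step 1: the plan's own figures.** Take u = 7.

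- f² = .21: λ = .21 × 110 = 23.1, power 94.7% (plan: > 94%).
- f² = .14: λ = .14 × 110 = 15.4, power 80.1% (plan: 80%).

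One setting therefore matches both stated figures when f² is set equal to the .21 ceiling. However, at f² = .21 every test from 1 df (99.7%) to 7 df (94.7%) satisfies > 94%, so this match does not identify the calculation.

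**Step 2: the 1-df test of a single interaction.** N = 110, alpha .05:

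| f² | λ = f² × 110 | Power |
|---|---|---|
| .21 | 23.1 | 99.7% |
| .114 | 12.54 | about 94% |
| .10 | 11.0 | 91% |
| .073 | 8.03 | 80% |
| .05 | 5.5 | 64% |
| .04 | 4.4 | 54.7% |
| .02 | 2.2 | 31% |

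Power reaches 94% only from about f² = .114 upward. Since .114 / .21 = .54, the claim fails over roughly the lower half of the stated range, even on this most favourable test.

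**Step 3: the f² < .04 sentence.** At f² = .04, power is 54.7%. Because .04 is itself a ceiling, 55% is a maximum. At alpha .10 it is 67%, still far below 94%. For scale, 80% power at f² = .04 would need 199 completers (1 df, alpha .05).

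**Step 4: the lower-bounded interactions.** At f² = .37, power with 110 completers is above 99% for every df from 1 to 7. The > 94% claim therefore holds for f² > .37, > .81 and > 1.11, taking the pilot values at face value.

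**The case against.** Several points on the other side have force.

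- **The two bounds do not contradict each other.** A value below .04 is also below .21. The .21 bound covers two interactions across several QST measures, so the larger value may belong to relief. The two sentences also use slightly different terms for drinking and for the outcome. This stands: the descriptions sit badly together and need clarifying, but they are not proven incompatible.
- **How the figure was produced is unknown.** A reader might infer from Step 1 that the ceiling was entered as the effect size in a 7-df test. The match is suggestive only: the predictor count is inferred, other combinations also give > 94%, and the pilot details are in a document not reproduced here.
- **The hypotheses do not depend on it.** A reader might infer that Aim 3 is underpowered. H7 concerns sex × dose and has its own statement (d > .90, > 80% power). H4 is the association of typical drinking with analgesia and is powered from correlations of .26 to .44. No numbered hypothesis tests sex × typical drinking or sex × relief.
- **The section is not uniformly optimistic.** It reports about 54% power for FH × dose and claims no power at f² < .04. That a null would be misread is therefore a possibility, not a certainty.

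None of this rescues the > 94% statement for the two interactions given only as f² < .21.

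**Conclusion.** The stated power is not supported by the plan's own figures for sex × typical daily drinking and sex × relief. On a 1-df test with 110 completers and assumed two-sided alpha .05, > 94% requires f² of about .114 or more; the plan says only that f² is below .21. If the f² < .04 sentence applies to sex × typical drinking, power for that term is at most 55% (67% at alpha .10).

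A reader might go further and quote the 7-df power at f² = .04. That would apply an interaction effect size to a test of the whole model and would not be the power of any planned interaction test.

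The consequence is limited to the sex-moderation terms in the Aim 1 regressions. The sample size, H4 and H7 are not called into question by this point. A related gap is that power is claimed for interactions with relief ratings, although no planned regression uses relief as a predictor.

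**What to change.** Revise the interaction paragraph of Power Analysis as follows.

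1. Restrict > 94% to the interactions with stated lower bounds (f² > .37, > .81, > 1.11), subject to item 4.
2. For sex × typical daily drinking and sex × relief, give the pilot point estimates separately, with the outcome measure named. State power for the test actually planned, for example: with 110 completers and two-sided alpha .05, a 1-df interaction test has 94% power at f² = .114, 80% at .073 and 55% at .04. Confirm the alpha.
3. Reconcile the f² < .21 and f² < .04 sentences. If < .04 is right for sex × typical drinking, state that power for it is at most 55%.
4. Drop the relief interactions from the power claim, including FH × relief, unless a regression with relief as a predictor is planned. If it is, add it to Data Analysis Strategy, Aim 1.

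Items 1 to 3 change wording only; their cost is a less favourable stated power for one or two secondary terms. Dropping relief under item 4 is also wording; adding a regression would be a small addition to the analysis plan. No change to sample size or design is needed.

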relief from alcohol, and SEAS measures (i.e., HIGH+, HIGH-, LOW+, and LOW-; Morean et al., 2013, 2015) as dependent variables. Demographic, personality/affective (i.e., BDI/STAI/IRQ/NEO-derived neuroticism), and biomedical (i.e., menstrual phase for female participants, sleep quality) variables will be included as covariates should any be found to correlate significantly with magnitude of alcohol analgesia or relief ratings. A main effect of FH status such that FH+ individuals have greater magnitude of alcohol analgesia (i.e., greater increases in pain threshold/tolerance and decreases in pain intensity ratings), more positive/fewer negative subjective alcohol effects, and stronger expectancy of pain relief from alcohol consumption will be interpreted as evidence in support of H1 and H3. Lower ratings of alcohol-related relief from pain in FH+ individuals will provide support for H2.

To determine the independent contributions of expectancies and typical drinking behavior to alcohol analgesia, these measures will be included as independent variables in separate multiple regression analyses including interaction vectors with sex and FH, with magnitude of alcohol analgesia (e.g., increased pain threshold or reduction in pain intensity ratings) as the dependent variable. They will then be entered into simultaneous regression analysis to assess independence of their effects. A positive association between typical drinking and analgesic response to alcohol will provide support for H4. Risk of Type I error will be mitigated through the use of Tukey's HSD. Although not a primary aim, the relationship between individuals' rate of rise of BAC following alcohol consumption and magnitude of alcohol analgesia will be examined in exploratory analyses. For FH+ participants, potential effects of the sex of affected parents and concordance with the participants' sex (i.e., sex-matched vs. unmatched pairs) will also be assessed.

Aim 2. Imaging functional correlates of alcohol analgesia and its modulating factors.

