H5, that alcohol administration will be associated with disruption of BOLD activation in/between regions associated with affective and cognitive aspects of pain processing during application of heat pain stimuli, and H6, that this disruption will be stronger among FH+ individuals, especially within motivation-related structures/circuits, will be evaluated using a two-part process. For all analyses described, motion will be controlled for at the individual subject level (i.e., first level) by including all six movement parameters (x/y/z translation, pitch/roll/yaw) and outlier volumes (determined using the Artifact Reduction Toolbox) as nuisance covariates. We will also co-vary for mean cerebral blood flow measured using pCASL-based resting state scans. Familywise error will be controlled for all analyses using false discovery rate correction (FDR; Benjamini and Hochberg, 1995) at $p < .05$.

Resting-state analyses: Pre-processed resting-state data will be analyzed using hybrid ICA-seed-based fcMRI analyses (Kelly et al., 2010). For this approach, independent components analysis (ICA) and seed- based correlations are used in tandem. First, ICA will be used to empirically derive a priori regions of interest (ROIs) based on resting-state networks identified from the study's participants. Networks of particular interest in this study include those associated with processing of nociceptive stimuli and those that

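### The stated sensitivity for the FH × sex × predictor interaction (f² > .14 at 80% power) is not that of the single 1-df term, which at two-sided .05 is about f² = .073

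*Combined protocol and SAP*

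**What the plan says.** All the power figures are in section 6, Power Analysis, of the combined protocol and SAP.

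- **Three-way interactions.** The plan offers a sensitivity figure in place of a pilot estimate: effect sizes of the FH × sex × predictor "interactions could not be assessed given our limited sample; however, we anticipate sensitivity to detect an interactive" f² above .14, at 80% power for the recruitment target. No numerator df, predictor count or alpha goes with it.
- **Two-way interactions.** Power above 94% is claimed for each of a set of interactions. The weakest in that set are those of sex with typical daily drinking and with relief ratings, printed as f² < .21.
- **Simple correlations.** The pilot showed "small-to-moderate correlations between expectancy of pain relief from alcohol, ratings of pain relief, and typical daily drinking" and reductions in pain sensitivity, with r between .26 and .44. About 80 to 99% power is expected for these.
- **Sample and sidedness.** "our targeted sample of 110 completers will provide" the power quoted for the pain measures, and "Power analyses were performed assuming two-tailed hypothesis tests".
- **Model.** The Data Analysis Strategy for Aim 1 enters expectancies and typical drinking in "separate multiple regression analyses including interaction vectors with sex and FH", and then together in a simultaneous regression.

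**The concern.** FH (+/−) and sex each have two levels, and each predictor is a single score. Their three-way interaction is therefore one product term, tested on 1 df. A minimum detectable f² of .14 looks too large for a 1-df test in 110 people. In the same section, about 80% power is attached to r = .26, which is an f² of roughly half that size.

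The sentence is the only power information the plan gives for these three-way terms. A reader who uses it to interpret a null result would treat effects with f² between about .07 and .14 as beyond the design's reach. If the 1-df calculation is right, power over that range is 80 to 97%.

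**Working it through.** **Inputs**

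- N = 110 completers (Power Analysis; under Participants the recruitment is planned "with the aim of obtaining 110 completers; 55 women").
- Two-sided tests (Power Analysis).
- Alpha = .05. This is an assumption: no alpha is given for the behavioural regressions. The only .05 in the plan is the imaging correction, "FDR; Benjamini and Hochberg, 1995) at $p < .05".
- Seven model terms: 3 main effects, 3 two-way products, 1 three-way product. This is inferred from the description of the regressions. Error df v = 110 − 7 − 1 = 102.

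**Formula.** Noncentral F with noncentrality λ = f² × N, numerator df u and denominator df v. Power is the probability that this variable exceeds the central-F critical value at alpha.

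**Step 1: reproduce the plan's .14** (N = 110, v = 102, alpha .05)

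| Numerator df | f² at 80% power | Power at f² = .14 (λ = 15.4) |
|---|---|---|
| 1 (single three-way term) | .0727 | 97.3% |
| 3 | .103 | 91.4% |
| 4 | .114 | 88.4% |
| 6 | .132 | 82.8% |
| 7 (all model terms) | .1396 | 80.1% |

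Of these, only the 7-df row gives .14. Reading the recruitment target as the 220 recruited does not help: the values become .036 (1 df) and .067 (7 df).

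**Step 2: check the 7-df origin against a second printed figure.** At f² = .21, λ = .21 × 110 = 23.1. Power is 94.7% on 7 df and 99.7% on 1 df. The plan prints > 94%, so two separate figures agree with a 7-df calculation.

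**Step 3: the 1-df term.** With u = 1 and v = 102, 80% power is reached at f² = .0727 (λ = .0727 × 110 = 8.0). At f² = .073 power is 80.1%. The ratio to the printed value is .14 / .073 = 1.9. Under the alternative convention λ = f² × (u + v + 1), the value is .077.

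**Step 4: consistency check with the correlations.** f² = r² / (1 − r²) = .0676 / .9324 = .0725 at r = .26. Power on 1 and 108 df is 79.9% (78.6% by Fisher's z), which agrees with the plan's figure of about 80%. At r = .44, f² = .1936 / .8064 = .240 and power is 99.9%. The correlation figures are therefore sound, and they put 80% power for a 1-df effect near .073.

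**Step 5: sensitivity to alpha** (1 df, v = 102)

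| Alpha | f² at 80% power |
|---|---|
| .05 | .073 |
| .025 | .089 |
| .0167 (.05/3, three predictors) | .098 |
| .01 | .110 |
| .005 | .126 |
| .001 | .164 |

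A single term needs .14 only at an alpha between .005 and .001, which the plan specifies nowhere.

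**The case against.** The strongest reply is that the printed statement remains true as a floor. At f² = .14 the 1-df term has 97.3% power, so the design delivers at least what is promised, and no sample size or test changes. That stands: the error is in the safe direction.

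The 7-df origin cannot be read off the page. The plan gives no df or alpha and refers to a grant document for the pilot detail. That also stands, and the most that can be said is that .14 appears to be a whole-model value. The .073 is likewise conditional on alpha .05. If the three three-way products were tested as a block in the simultaneous regression, the 3-df value would be .103. None of these alternatives reaches .14.

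The FH × sex × predictor interaction is also not a numbered hypothesis: H4 concerns typical drinking, and Empirical Question 1 concerns sex by FH by dose. This limits the practical weight of the point.

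A reader might infer three stronger things that the documents do not support:

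- **That the r = .26 figure contradicts the .14.** It is a zero-order correlation in a different model, and both statements can hold as lower bounds. It serves only as a consistency check.
- **That the regression power figures in general were computed for the wrong test.** The correlation powers reproduce on 1 df, and the > 94% floor at f² = .21 stays true on 1 df.
- **That the study is underpowered for these terms.** The discrepancy runs the other way.

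**Conclusion.** The point holds in a limited form. An f² of .14 at 80% power is not the sensitivity of the single FH × sex × predictor term. Assuming two-sided alpha .05, 110 completers and seven model terms, that term has 80% power at f² = .073 and 97% at .14. The minimum detectable effect is thus overstated about twofold at alpha .05, and by less at a stricter alpha (.14 against .089 at .025 and .110 at .01). The printed value most likely belongs to a joint test of all seven terms. Such a test can be significant through main effects alone, so it does not describe sensitivity to an interaction. That attribution is an inference resting on two matching figures (80.1% at .14 and 94.7% at .21). The mismatch with a 1-df test does not depend on it.

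**What to change.** Replace the sensitivity sentence in the Power Analysis with: *With 110 completers, two-sided alpha .05 and a seven-term model, a single FH × Sex × predictor term (1 df) has 80% power at f² = .073 and 97% at f² = .14.* If a different alpha or number of terms was intended, state it and recompute. If a whole-model test was intended, keep .14, give its 7 numerator df, and stop calling it an interaction effect.

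Restate the two-way interaction power at f² = .21 on the same 1-df basis (99.7%); the > 94% floor need not be withdrawn. The correlation power figures need no change.

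The cost is a sentence or two in the power section, with no change to design, sample size or analysis.
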